6.2. Immunogenicity

6.2.1. Sampling Timepoints

Samples to assess the generation of antibodies to daratumumab (immunogenicity) will be obtained from all subjects in the DRd group at Cycle 1 Day 1 predose, End-of Treatment, and Post-Treatment Week 8. In addition, any time an infusion-related reaction is observed during the study, an unscheduled blood sample should be drawn as soon as possible after the reaction for potential immune response analysis.

6.2.2. Analysis Methods

The incidence of anti-daratumumab antibodies (immunogenicity) will be summarized for all subjects who receive a dose of daratumumab and have appropriate samples for detection of antibodies to daratumumab. In addition, subjects who are positive for antibodies to daratumumab will also be listed.

6.3. Pharmacokinetic/Pharmacodynamic Analyses

If sufficient data are available, other pharmacokinetic/pharmacodynamic modeling may be performed, including exploring the relationship between serum concentrations of daratumumab and endpoints of clinical efficacy. If analysis is conducted, details and results of the analysis will be presented in a separate report.

7. BIOMARKER

Biomarker studies are designed to identify markers predictive of response (or resistance) to daratumumab. Planned analyses are based on the availability of clinically valid assays and may be deferred if emerging study data show no likelihood of providing useful scientific information. Results of biomarker analyses may be presented in a separate report.

Blood samples will be drawn from all subjects in both treatment groups to better understand the mechanism of action and mechanism of resistance of daratumumab. Minimal residual disease (MRD) will be assessed from bone marrow aspirates for all subjects who achieve a CR/sCR. Molecular subtyping will be done to evaluate daratumumab response rates in high-risk multiple myeloma subpopulations.

7.1. Minimal Residual Disease (MRD)

Bone marrow aspirates will be collected to monitor MRD in those subjects who attain or suspect to have a CR/sCR. MRD will be monitored using next generation sequencing (NGS) on bone marrow aspirate.

7.1.1. Sampling Timepoints

Samples are requested at time of suspected CR/sCR and at 12, 18, 24 and 30 months post C1D1 (+/-1 month). If one of these time points occurs within 1 month of suspected CR, a repeat bone marrow will not be requested. These bone marrow tests will only be required if patient's response is near CR or better by blood and urine evaluations (for detail timepoint refer to protocol Section 9.2.1.5).

7.1.2. Analysis Methods

Details on MRD negativity rate analyses are described in Section 4.3.4.

In addition, to evaluate the relationship between MRD negativity and clinical endpoints (e.g. PFS) may be explored.

7.2. Molecular Subtyping

7.2.1. Sample collection and characterization

Viable, frozen CD38+ bone marrow aspirate samples were collected at baseline for DNA/RNA sequencing analysis. Peripheral blood mononuclear cell (PBMC) samples were collected at baseline to use as controls.

7.2.2. Molecular Subtypes

A portion of the bone marrow aspirate samples collected as specified in the Section 7.2.1 will be utilized for translocation/mutation/genomic analysis using exome-sequencing and RNA-sequencing to assess whether specific molecular subgroups having chromosomal aberrations such as del17p, t(4;14), t(14;16), are responsive to daratumumab treatment. PBMC samples will be sent for exome sequencing and used as controls for mutation and copy number analysis.

7.2.3. High-risk/Standard-risk Molecular Subgroup Analysis

High-risk and standard-risk molecular subgroups have been defined in Section 2.9.

To determine if daratumumab combined with Rd (DRd) will lead to improved clinical responses in high-risk molecular subgroups, the following exploratory analysis will be conducted by using the similar analysis methods specified in Sections 4.3.1.2 and 4.2.2.

- To evaluate ORR and MRD negativity rate for subjects in high-risk molecular subgroup and subjects with specific molecular subtyping such as del17p, t(14;16), t(4;14)
- To evaluate PFS and OS for subjects in high-risk molecular subgroup and subjects with specific molecular subtyping such as del17p, t(14;16), t(4;14)

If subgroup size allows, these results will also be compared with the subjects treated with DRd in the standard-risk molecular subgroup, to explore whether subjects treated with DRd in high risk molecular subgroup will have similar clinical outcome as subjects in standard risk subgroup.

8. MEDICAL RESOURCE UTILIZATION

Medical resource utilization (excluding study infusion administration) will be descriptively summarized by treatment group. Frequencies of hospitalization, outpatient visits, type of hospitalization or outpatient visit, reasons for hospitalization or outpatient visit, durations of hospitalization or outpatient visit will be calculated and tabulated.

REFERENCES

- 2. Rajkumar SV, Harousseau J-L, Durie B, et al. Consensus recommendations for the uniform reporting of clinical trials: report of the International Myeloma Workshop Consensus Panel 1. Blood. 2011; 4691-4695.

ATTACHMENTS

ATTACHMENT 1: Additional Exploratory Analysis to Support HEMAR

1. DEFINITION OF SUBGROUPS

Subgroup analyses will be performed using the criteria listed below to determine whether the treatment effect is consistent among subgroups. Analyses will be conducted for the ITT population and for the following subgroups:

- For subjects who reached CR/sCR as their best response
- For subjects who reached VGPR as their best response
- For subjects who reached PR as their best response
- For subjects who reached PD as their best response
- For subjects who had baseline ECOG of 2
- For subjects who achieved MRD negativity (10⁻⁴, 10⁻⁵ and 10⁻⁶)

Subgroup analyses will be performed if data warrants.

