4.1. Analysis Specifications

4.1.1. Level of Significance

All statistical hypothesis tests and 95% confidence interval presented will be 2-sided.

The primary hypothesis is to be tested at the 0.05 significance level (overall). The exact significance level at the second interim analysis is to be determined by the observed number of events per the O'Brien-Fleming alpha spending function. Assuming 234 PFS events are observed at the second interim analysis, the alpha to be spent will be 0.0076 (2-sided) for the interim analysis and 0.0476 (2-sided) for the primary PFS analysis (390 PFS events occur). If the observed two-sided p-value is smaller than this significance level as specified above, the superiority of DRd versus Rd with respect to PFS will be established.

If the primary endpoint of PFS is statistically significant, the following secondary endpoints ordered below will be sequentially tested, each with an overall two-sided alpha of 0.05, by utilizing a hierarchical testing approach as proposed by Tang and Geller (1999) that strongly controls Type I error rate:

- 1) CR or better rate
- 2) VGPR or better rate
- 3) MRD negativity rate (10⁻⁵)
- 4) Overall response rate (ORR)
- 5) Overall survival (OS)

These secondary endpoints will be tested at the 2nd IA and the primary PFS analysis. The primary PFS analysis will be skipped if PFS is positive at the 2nd IA. If this is the case, the protocol will be amended to add an analysis for secondary endpoints at a similar timing as the planned primary PFS analysis (note that OS will also be tested at its protocol-specified final analysis). The significance level at the second interim and the primary PFS analyses will be determined by the alpha-spending function specific to endpoints:

- For ORR, VGPR or better rate, CR or better rate, and MRD negativity rate (10⁻⁵), the information fraction is expected to be 80% at the 2nd IA. The O'Brien-Fleming alphaspending function as implemented by the Lan-DeMets method will be used for alphaspending: 0.0244 (two-sided) at the 2nd IA and 0.0428 (two-sided) at the primary PFS analysis.

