4.3.1. CR or Better Rate

4.3.1.1. **Definition**

CR or better rate is defined as the proportion of subjects with a response of CR or better (i.e., CR or sCR) based on the computerized algorithm, according to IMWG response criteria, during or after the study treatment.

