4.3.3.1. Definition

MRD negativity rate is defined as the proportion of subjects who have negative MRD at any time point after the date of randomization and prior to subsequent antimyeloma therapy. MRD

positive subjects include subjects of which all tested results were found to be MRD positive, or indeterminate, or unavailable (calibration failure or missing).

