4.4. Subgroup Analysis of Efficacy Endpoints

For assessment of internal consistency and investigation of homogeneity of the treatment effect across subgroups, subgroup analyses of the primary and selected secondary efficacy endpoints will be conducted based on pre-specified subgroups defined in Section 2.10.

A forest plot of subgroup analysis on PFS and selected secondary endpoints (e.g. ORR) will be generated, respectively.

Additionally, the primary endpoint of PFS and secondary endpoint of TTP may be explored by responder vs non-responder for each treatment group.

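### SAP Attachment 1 judges consistency of the treatment effect within best-response and MRD groups, which are outcomes of treatment, so these by-arm comparisons cannot serve that aim

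*SAP*

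**What the plan says.** SAP Attachment 1, section 1, gives the purpose of its subgroup analyses as "to determine whether the treatment effect is consistent among subgroups". It lists six groups. Four are best-response categories, the first being "For subjects who reached CR/sCR as their best response", followed by VGPR, PR and PD. A fifth is "For subjects who achieved MRD negativity" at three thresholds. Only one is a baseline factor: "For subjects who had baseline ECOG of 2".

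Section 2 of the attachment applies these groups, together with the baseline groups of SAP 2.10, to PFS, TTP, time to subsequent treatment, PFS2, OS, time to best response and DOR. The stated method is Kaplan-Meier estimation by treatment arm with descriptive statistics.

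A related sentence in SAP 4.4 says that PFS and the "secondary endpoint of TTP may be explored by responder vs non-responder for each treatment group".

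Neither place mentions a landmark, a time-dependent covariate, a principal-stratum method or a caution about interpretation.

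**The concern.** A subgroup can be used to check consistency of a treatment effect because, within a group fixed before randomisation, the arms are still comparable. Best response and MRD status are not fixed before randomisation, and daratumumab is expected to change them. If DRd moves subjects of intermediate prognosis into CR who would have reached only VGPR on Rd, the DRd subjects in CR have on average a worse underlying prognosis than the Rd subjects in CR. The same applies further down the scale. The difference between the curves then mixes treatment effect with selection, and a reader cannot separate the two.

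There is a second problem for endpoints timed from randomisation. A subject must remain in follow-up and progression-free long enough to reach the response or give the negative MRD sample. That time is guaranteed for everyone in the group, so the curves start too high.

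At stake is how these tables would be read. Curves lying close together in each response category could be taken to mean that daratumumab adds little once response is known, or that the effect is inconsistent, when neither follows.

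**Working it through.** **1. Is membership decided after randomisation, and is treatment expected to affect it?**

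- SAP 4.3.3.1: "MRD negativity rate is defined as the proportion of subjects who have negative MRD at any time point after the date of randomization" (and before subsequent therapy).
- SAP 4.3.1.1: "CR or better rate is defined as the proportion of subjects with a response of CR or better", reached during or after study treatment.
- SAP 4.1.1: once PFS is significant, "the following secondary endpoints ordered below will be sequentially tested". The list is CR or better, VGPR or better, MRD negativity, ORR and OS.

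So the variables that define the groups are the same variables the hierarchy tests for a difference between arms. By contrast, the subgroups in SAP Table 1 are all baseline-defined.

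**2. The plan's own figures.** Attachment 1 gives no figure for these groups. The design inputs used below (protocol 11.2: control median 24 months, HR 0.75, 390 events, 21-month accrual, 24-month follow-up, 5% annual dropout, N about 730) reproduce:

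- Schoenfeld: 4 × (1.960 + 0.842)² / (ln 0.75)² = 380 events.
- Freedman: (1.75/0.25)² × (1.960 + 0.842)² = 385 events.
- Power at 390 events: 81.1%.
- Event probabilities of 0.588 (Rd) and 0.490 (DRd) give N = 390/0.539 ≈ 724.

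These figures are not in dispute.

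**3. A hand check of the mechanism.** Assume prognosis u is uniform on (0, 1) and median PFS is 24·exp[2.4(u − 0.5)] months in both arms, so there is no treatment effect on PFS. Let CR occur when u > 0.75 on Rd (25%) and u > 0.52 on DRd (48%). Mean u among complete responders is 0.875 on Rd and 0.76 on DRd. Median PFS at those means is 24·e^0.9 = 59.0 and 24·e^0.624 = 44.8 months. The hazard ratio is about 59.0/44.8 = 1.32 against DRd, with no true effect.

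Simulating this model, with several assumed VGPR cut-offs, gave HRs of 1.31–1.50 (CR), 1.64–1.90 (VGPR) and 1.26–1.40 (PR or worse). It is close to a worst case because response is a perfect marker of prognosis. Adding noise to response (SD 0.3 on the u scale) lowered these to 1.18–1.21, 1.39–1.55 and 1.15–1.22. With SD 0.6 they were 1.10–1.13, 1.20–1.23 and 1.10–1.14.

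**4. A second model with a weaker link.** Prognosis u is standard normal and the PFS hazard is (ln 2/24)·exp(−γu)·HR^arm. The response score is √0.5·u + √0.5·noise + shift × arm. Cut-points give 20% SD/PD, 30% PR, 25% VGPR and 25% CR on Rd. Design accrual, follow-up and dropout apply, with 400,000 subjects per scenario. The response rates, γ and shift are assumptions.

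| True HR | DRd CR rate (shift) | γ | All | SD/PD | PR | VGPR | CR |
|---|---|---|---|---|---|---|---|
| 1.00 | 25% (0) | 0.4 | 1.00 | 1.00 | 1.01 | 0.99 | 0.99 |
| 1.00 | 25% (0) | 0.8 | 0.99 | 0.99 | 1.00 | 1.01 | 0.98 |
| 1.00 | 36% (0.3) | 0.4 | 0.99 | 1.07 | 1.08 | 1.07 | 1.05 |
| 1.00 | 36% (0.3) | 0.8 | 0.99 | 1.12 | 1.14 | 1.15 | 1.12 |
| 1.00 | 47% (0.6) | 0.4 | 1.00 | 1.14 | 1.15 | 1.17 | 1.13 |
| 1.00 | 47% (0.6) | 0.8 | 1.00 | 1.27 | 1.31 | 1.35 | 1.23 |
| 0.75 | 25% (0) | 0.4 | 0.77 | 0.76 | 0.76 | 0.76 | 0.76 |
| 0.75 | 25% (0) | 0.8 | 0.79 | 0.79 | 0.78 | 0.78 | 0.76 |
| 0.75 | 35% (0.3) | 0.4 | 0.76 | 0.80 | 0.82 | 0.82 | 0.81 |
| 0.75 | 35% (0.3) | 0.8 | 0.79 | 0.87 | 0.91 | 0.89 | 0.87 |
| 0.75 | 47% (0.6) | 0.4 | 0.76 | 0.85 | 0.88 | 0.88 | 0.85 |
| 0.75 | 47% (0.6) | 0.8 | 0.79 | 1.00 | 1.04 | 1.02 | 0.97 |

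The zero-shift rows show no bias, so the distortion comes from treatment changing group membership. The HR 0.75 rows are nearer to the trial's design hypothesis: a benefit present in every subject is diluted, or disappears, in every category.

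**5. Limits of the models.** Both models show the selection effect only. Neither includes immortal time or an MRD group, and the first merges PR with anything worse.

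**The case against.** The strongest reply is that this is a set of exploratory tables, run only if the data warrant it, with descriptive Kaplan-Meier output. It lies outside the alpha hierarchy and is separate from the Table 1 subgroups. All of that is correct and limits the importance of the point. It does not rescue the stated aim: by-arm curves inside an outcome-defined group carry the same selection whether or not a p-value is attached.

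Four stronger readings are tempting, and the documents do not support them.

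- A reader might infer that the SAP plans hazard ratios in these groups. Attachment 1 names none for them; it names hazard ratios only for safety endpoints, in section 4. Protocol 11.3 does equate treatment effect with the hazard ratio, so one might be derived, but it is not specified.
- A reader might take SAP 4.4 as the same defect. That analysis is optional and made within each treatment group, so it is not a comparison of DRd with Rd. Only the immortal-time problem applies there.
- A reader might conclude that these tables will go into health-economic submissions. The attachment title says only that the analyses support HEMAR, and I found no expansion of the term.
- A reader might expect spurious benefit as readily as spurious harm. The models above show only spurious harm or dilution of benefit, and the direction depends on assumptions about how response and prognosis are linked.

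**Conclusion.** The point holds for the best-response and MRD groups in Attachment 1. Used as the SAP states, they give non-randomised comparisons that cannot show whether the treatment effect is consistent. The baseline ECOG 2 group is sound.

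The size is not computable from the documents, and no single figure should be quoted. With no true PFS effect, the within-category HR ranged from about 1.05 (small response shift, weak prognostic link) to about 1.9 (response a perfect marker of prognosis). With a conditional HR of 0.75 it ranged from about 0.80 to 1.04, against 0.76 to 0.79 in all subjects. These ranges rest on assumed response rates, response shifts and prognostic effects.

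It would be wrong to read this as a threat to the trial's main results. The primary PFS analysis and the tested secondary endpoints do not use these groups. This is a change that should be made to an exploratory attachment.

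**What to change.** In Attachment 1, section 1, limit the consistency aim to baseline-defined groups (ECOG 2 and the SAP Table 1 groups), and remove the best-response and MRD groups from that list.

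If outcome by response or MRD is wanted, report it within each arm and label it prognostic association. Use one of two methods:

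- A landmark analysis among subjects still event-free and in follow-up at the landmark, with status fixed at that time. Set the landmark after the relevant assessment window closes. The 12-month MRD sample in SAP 7.1.1 has a window of one month either side, counted from C1D1, so a landmark at exactly 12 months would cut through it. Subjects who first become MRD negative at a later sample would count as not negative, which should be stated.
- Response or MRD as a time-dependent covariate, which avoids choosing a landmark.

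SAP 7.1.2 already allows the relationship between MRD negativity and PFS to be explored, so the MRD part fits there. In SAP 4.4, keep the responder analysis within arm and add the same landmark or time-dependent handling.

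The cost is minor SAP wording and one extra analysis of existing data. The by-arm tables in response and MRD groups would no longer be available as evidence on treatment effect.

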2. TIME-TO-EVENT ENDPOINTS FOR SUBGROUP ANALYZES

Kaplan-Meier estimates will be used to estimate distribution of time to event by treatment arm based on all ITT population. Data will be calculated and summarized with descriptive statistics. The following time-to-event endpoints will be analyzed by pre-defined subgroups as defined in section 2.10 and in section 1, Appendix:

- PFS
- TTP
- Time to subsequent antimyeloma treatment
- PFS2
- OS
- Time to best response
- DOR

2.1. Subgroup Analysis by Center for PFS, OS and EQ-5D and EORTC QLQ C30

3. EXPOSURE ADJUSTED INCIDENCE RATES (EAIR)

3.1. Restriction on the first event

The analysis restricts on the occurrence of the first event per patient and ignores the existence of later (multiple) events as these cannot be assumed to occur independent of previous events (e.g.: patients suffering from infections may have in general a higher risk of having other complications and may even have a higher risk of getting other infections). The occurrence of multiple events is subject to another analysis considering the absolute number of adverse events per patient.

For these reasons the EAIR should be interpreted as 'rate until the first event occurs'. Rates estimated from several patients can be averaged on the level of a preferred term (PT), of a system organ class (SOC), or on a global level (see below).

The interpretation of EAIRs is simple and consistent on the preferred-term level only, and can be expressed as "Average number of TEAEs per preferred-term emerging per person-month of exposure".

The aforementioned considerations apply in the same way to EAIRs estimated on the global level: when EAIRs are collapsed into the global estimate (first analyses), the estimate can be interpreted as the "Average number of TEAEs emerging per person-month and PT", because estimation has been performed on a 'per PT'-basis (per average or typical PT among all PTs).

Comparing EAIRs on the level of the SOC or on the global level involves data destruction because a patient's information is reduced to the first TEAE only (and possibly to a TEAE of marginal relevance among many TEAEs with higher clinical relevance).

The EAIR analysis focuses on the 'speed' by which TEAEs emerge. The analysis restricts on the first event of a patient because independence of TEAEs cannot be assumed. The necessity to restrict on the first event entails considerable data destruction when deriving SOC-specific EAIRs or the EAIR on a global level. To overcome this, the 'per PT'-analysis, which is reported in both Tables identically, is preferable.

Comparing EAIRs between the analyses outlined below on a SOC-specific or a global level demonstrates that the 'per PT'- method makes the interpretation of results more difficult. However, it can be suggested that this method provides a more robust approach when the two treatment arms are to be compared on a SOC-specific or global level. A t-Test like comparison of PT-specific estimates between the two treatment arms may provide a more robust, comprehensive and easy-to-communicate way of visualizing and comparing results.

3.2. Duration of exposure: censored & non-censored

The incidence rate for a patient is derived from the duration of exposure to treatment of that patient. When averaging incidence rates, a patient's duration of exposure is given either A) by the time when the event has occurred (non-censored data), or B) by the total duration of treatment in case the patient does not show the adverse event in question (censored data). Depending on whether a patient has an adverse event or not, the duration of exposure enters the denominator in its non-censored or censored form, respectively.

3.3. Incidence rate per patient

The incidence rate for a specific event of a patient *i* is the reciprocal of time *t* when the first event occurs:

$$EAIR_i = \frac{1}{t_i}.$$

3.4. Average EAIR

The EAIR averaged over all patients is

$$EAIR = \frac{\sum_{i=1}^{n} TEAE_{i}}{\sum_{i=1}^{n} t_{i}},$$

whereby

- a) a TEAE enters the sum in the nominator unweighted ($TEAE_i = 1$, otherwise $TEAE_i = 0$), and
- b) the duration of exposure enters the denominator as described before: $t_i = \begin{cases} time\ of\ TEAE\ if\ occurring\ (non\text{-censored data})\\ total\ duration\ of\ treatment\ if\ no\ event\ occurs\ (censored\ data) \end{cases}.$

3.5. EAIRs on the level of a SOC and on the global level on a 'per-PT' basis

3.5.1. Average EAIR per PT

The EAIR for a specific PT is an average over all patients, i.e.

$$EAIR_{PT} = \frac{\sum_{i=1}^{n} TEAE_{PT,i}}{\sum_{i=1}^{n} t_{PT,i}},$$

whereby the number of TEAEs and durations of exposure enter the nominator and the denominator.

3.5.2. Average EAIR per SOC

The average *EAIR* per SOC considers the first event of each patient within the SOC. The denominator includes the exposure time of each adverse event of all PTs within the SOC, per patient, i.e.

$$EAIR_{SOC} = \sum_{i=1}^{n} TEAE_{SOC,i} \sum_{PT=1}^{n \ PTs \ per \ SOC} \frac{1}{t_{PTi}}$$

where $TEAE_{SOC,i}$ is the first event per patient per SOC and $t_{PT,i}$ is the exposure time for a specific preferred term of a given patient.

Note: This *EAIR* is an incidence rate per *average* (or typical) preferred term in that SOC (cf. 3.6.1).

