3.5.3. Average EAIR on a global level

The average *EAIR* on a global level only considers the first event per patient across all events. The denominator includes the exposure times of all PTs, i.e.

$$EAIR_{global} = \sum_{i=1}^{n} TEAE_{i} \sum_{PT=1}^{n} \frac{1}{t_{PT,i}},$$

where $TEAE_i$ is the first event of a patient overall and the $t_{PT,i}$'s are PT-specific exposure times of that patient.

Note: This EAIR is an incidence rate per average (or typical) preferred term.

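### The per-PT exposure-adjusted rates at SOC and global level count one event per patient over exposure summed across all preferred terms, so they fall with longer follow-up and favour the longer-treated arm

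*SAP*

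**What the plan says.** SAP Attachment 1 holds additional exploratory analyses to support HEMAR. It gives two sets of exposure-adjusted incidence rates above the level of the single PT.

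- **Per-PT set, SOC level (3.5.2).** The numerator "considers the first event of each patient within the SOC". For the denominator: "The denominator includes the exposure time of each adverse event of all PTs within the SOC, per patient".
- **Per-PT set, global level (3.5.3).** The rate "only considers the first event per patient across all events". For the denominator: "The denominator includes the exposure times of all PTs". The note adds: "This EAIR is an incidence rate per average (or typical) preferred term". The SOC note in 3.5.2 says the same for the PTs in that SOC.
- **Exposure for a PT that never occurs (3.2).** It is given "by the total duration of treatment in case the patient does not show the adverse event in question (censored data").
- **Second set (3.6.2 and 3.6.3).** One first event per patient, divided by one corresponding exposure time. These sections also remark that the denominator of the per-PT set varies with how many PTs there are.
- **Recommendation (3.1).** The SAP concedes that the per-PT method makes SOC and global results harder to interpret. It then puts forward, in hedged terms, that "this method provides a more robust approach when the two treatment arms are to be compared" at those levels. The next sentence reads: "A t-Test like comparison of PT-specific estimates between the two treatment arms may provide a more robust" and easily communicated comparison.

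**The concern.** Numerator and denominator count different things. Once a patient has had one event in the SOC, the numerator is fixed at one. Every other PT in that SOC goes on adding exposure until it occurs or treatment stops. A rate built this way has to fall as treatment lengthens, even when the risk is constant.

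Exposure adjustment is there because the arms may be treated for different lengths of time. Treatment continues to progression or unacceptable toxicity (SAP 1.1), and the design expects later progression on DRd. An estimator that falls with exposure makes the longer-treated arm look safer, and 3.1 suggests it for the between-arm comparison.

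**Working it through.** **No figure to reproduce.** The documents give no numerical EAIR. The check is algebraic, with simulation as support.

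**Inputs**
- From the documents: median PFS on Rd of 24 months and a hazard ratio of 0.75 (SAP 1.3). With exponential PFS the DRd median is 24/0.75 = 32 months. These medians stand in for treatment duration.
- Assumed, not in the documents: K PTs, independent, each with constant hazard L. The base value is L = 0.01 per month; the range is 0.002 to 0.02, with K from 5 to 500.

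**One patient.** First event in month 2, no other event, a SOC of 4 PTs. Treated for 24 months: 1/(2 + 3×24) = 1/74 = 0.0135. Treated for 48 months: 1/(2 + 3×48) = 1/146 = 0.0068. The safety experience is the same and the rate is halved.

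**Fixed exposure T.** Expected numerator per patient: 1 − exp(−KLT). Expected denominator: K(1 − exp(−LT))/L. Hence

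rate = L(1 − exp(−KLT)) / [K(1 − exp(−LT))].

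This tends to L as T goes to 0 and to L/K as T grows. For K = 10 and T = 24: 0.01 × 0.9093 / (10 × 0.2134) = 0.0043, against a true per-PT rate of 0.0100.

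| L = 0.01 | 6 mo | 12 mo | 24 mo | 48 mo |
|---|---|---|---|---|
| K = 5 | 0.0089 | 0.0080 | 0.0066 | 0.0048 |
| K = 10 | 0.0078 | 0.0062 | 0.0043 | 0.0026 |
| K = 20 | 0.0060 | 0.0040 | 0.0023 | 0.0013 |

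**Exponential exposure, rate m = ln 2/median.** The rate becomes L(L + m)/(KL + m), with m = 0.02888 for Rd and 0.02166 for DRd.

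Equal true hazards, K = 20: Rd 0.01 × 0.03888/0.22888 = 0.00170; DRd 0.01 × 0.03166/0.22166 = 0.00143; ratio 0.84. K = 5 gives 0.90 and K = 50 gives 0.83. Over the assumed range of L and K the ratio runs from 0.77 to 0.94. The correct value is 1.00 throughout.

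**True DRd/Rd hazard ratio of 1.5, K = 10** (L = 0.015 against 0.01):
- Fixed exposure of 32 and 24 months: 0.00390/0.00426 = 0.92.
- Exponential exposure: 0.00320/0.00302 = 1.06.

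**Alternatives under the same model**
- 3.6.2 gives [KL/(KL + m)] / [1/(KL + m)] = KL, the SOC rate, whatever the follow-up.
- Summing first events per PT in the numerator gives [KL/(L + m)] / [K/(L + m)] = L, the average-PT rate, whatever K and the follow-up.
- In simulation with 200,000 patients per arm and equal hazards, the arm ratio was 0.998 to 1.002 for both, against 0.893, 0.845 and 0.825 for the prose of 3.5.2 at K = 5, 20 and 50.

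**The printed equation.** In the text available here, the equations in 3.5.2 and 3.5.3 show a sum of reciprocals 1/t, not division by a summed exposure. Simulated literally (K = 5, L = 0.01, median exposure 24 months), this gives about 136 with 365 patients, 312 with 730 and 1,570 with 3,650. It scales with sample size, so it is not a rate either.

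**The case against.** Much can be said for the SAP.

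- **PT-count dependence is disclosed.** 3.6.2 and 3.6.3 state it, and 3.1 warns of lost information and harder interpretation above PT level. A reader might infer that the SAP conceals this; it does not. What it leaves unsaid is the dependence on follow-up and the mismatch that makes the average-PT label wrong.
- **A sound estimator is already planned.** 3.6.2 and 3.6.3 cover the same levels, and Attachment 1, section 4, adds Kaplan-Meier curves and hazard ratios for adverse events because exposure may differ. This limits the harm. It does not support suggesting the other set as more robust.
- **The t-test-like comparison uses PT-specific rates.** Those in 3.5.1 and 3.6.1 are correctly formed. A reader might take the t-test as inheriting this defect; it does not. Its weakness is separate and minor: it treats PTs observed in the same patients as independent units, and the SAP says only that it may be useful.
- **The equation may be damaged by text extraction.** That is possible, so the figures above apply to the prose definition.
- **The size depends on the inputs.** Exposures of 30 against 16 months, for example, would give 0.68 for equal rates at K = 10 and L = 0.01, but nothing in the documents supports that gap.

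**Conclusion.** The concern holds for the SOC and global per-PT rates as the prose defines them. They are not average-PT rates, and they fall as follow-up lengthens. Under constant, independent PT hazards, the longer-treated arm is favoured whenever K exceeds 1. With 24 against 32 months as median exposure and L = 0.01, the distortion of an equal-risk comparison is about 10 to 17 percent (ratios 0.90 to 0.83 for K = 5 to 50), and 6 to 23 percent over the wider assumed range. Median PFS is only a proxy for treatment duration, and PT hazards and counts are assumed.

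A reader might infer that a real excess risk on DRd would be reversed. The documents do not support that as a general result: a true ratio of 1.5 shows as 0.92 or 1.06 depending on the exposure model, so strong attenuation is what can be said. Nor do they show that the main safety conclusions rest on this formula. SAP 5.3.2 allows an exposure-adjusted rate for infections but names no formula. The attachment is exploratory, and neither the primary endpoint nor any endpoint in the hierarchical testing uses it.

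**What to change.** - Use 3.6.2 and 3.6.3 for SOC and global rates and for comparing arms. Delete 3.5.2, 3.5.3 and the statement in 3.1 that the per-PT method is more robust.
- If an average-PT rate is still wanted, make the numerator the sum over PTs of first events per PT, keep the summed exposure as denominator, and correct the equation to match.
- In either case, check the equations in 3.5.2 and 3.5.3 against the original document.
- As a separate minor point, replace the suggested t-test-like comparison across PTs with rate ratios and confidence intervals computed over patients.

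The cost is small: the preferred option mostly removes text, and the replacement formulas are already specified in the SAP. No data collection or tested endpoint changes.
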